6.3.2 Replacement

Randomized patients who withdraw prematurely will not be replaced.

6.4 Patient identification

The patient number is a 9-digit number consisting of:

Digits 1 to 5 = Unique center number

Digits 6 to 9 = Current patient number within the center

7. Treatments

7.1 Treatments to be administered

Patients will be randomized 1:1:1 within 4 weeks after the Screening Visit to either:

1. Placebo arm: placebo and sham up-titration at weeks 2, 4, and 6
2. 10 mg arm: vericiguat, which will be started at 2.5 mg at randomization and up-titrated to 5 mg at week 2, and to 10 mg at week 4, with sham titration at week 6.
3. 15 mg arm: vericiguat, which will be started at 2.5 mg at randomization and up-titrated to 5 mg at week 2, to 10 mg at week 4, and to 15 mg at week 6.

Study drug treatment will be initiated after clinical stabilization, within 6 months after the onset of the qualifying HF decompensation, defined as HF hospitalization or IV diuretic treatment for HF without hospitalization. End of treatment is reached at visit 9 after 24 weeks of treatment.

Dose modification will depend on mean sitting SBP and the absence of symptoms indicative of hypotension before intake of the dose as described in Section 7.4. The intention of the protocol is to reach and maintain the target study drug dose upon uptitration. If the patient does not reach the 15 mg dose step by the time of the week 6 visit (42±3 days after randomization), or the dose is temporarily interrupted and when the investigator feels it is medically appropriate to resume it afterwards, uptitration should be considered at any subsequent visit at the discretion of the investigator according to the SBP criteria in Section 7.4.

If in the opinion of the investigator the patient does not tolerate the target dose of the study drug and presents symptoms of orthostatic hypotension, in addition to considering the reduction of the study drug the investigator should also consider the volume status, and whether there is a necessity to change the dose of diuretics. If such adjustment or discontinuation of concomitant diuretic or other medications (such as anti-hypertensive therapy, in the case of excessive blood pressure lowering) is not possible or does not resolve signs and symptoms of intolerance, the investigator may at any time during the course of the trial reduce the dose or interrupt study treatment in patients who no longer tolerate the current study drug dose.

Down-titration is possible at any time during the study if the investigator feels this is justified for safety reasons. Reasons for dose modifications (maintenance, increase, decrease, or interruption) will be collected at all planned or unscheduled visits. In case of temporary discontinuation or dose reduction after the titration period, up-titration is also possible at scheduled visits.

7.2 Identity of study treatment

Table 7-1: Identity of test drug

INN	vericiguat
Substance code number	BAY 1021189
Formulation	IR tablets
Strength	2.5 mg, 5 mg or 10 mg BAY 1021189

Table 7-2: Identity of matching placebos

INN	N/A
Substance code number	N/A
Formulation	Tablets
Strength	N/A

All study drugs will be labeled according to the requirements of local law and legislation. Label text will be approved according to the sponsor's agreed procedures, and a copy of the labels will be made available to the study site upon request.

For all study drugs, a system of numbering in accordance with all requirements of GMP will be used, ensuring that each dose of study drug can be traced back to the respective bulk batch of the ingredients. Lists linking all numbering levels will be maintained by the sponsor's clinical supplies quality assurance group.

A complete record of batch numbers and expiry dates of all study treatment as well as the labels will be maintained in the sponsor's study file.

7.3 Treatment assignment

Following a screening visit, eligible patients stabilized after a HF decompensation will be randomly allocated 1:1:1 via block randomization to one of the 3 equally sized groups (2 vericiguat groups, 1 placebo group) using IxRS and will receive treatment with study drug or placebo for 24 weeks. The IxRS will determine the kit number for the study site investigator or designee to select for the subject. Patients are to take 2 tablets once daily, preferably in the morning with food, throughout study drug treatment. In case patient is randomized in the afternoon first tablets can be taken then and should be continued the next day in the morning.

Patients will be randomized within 4 weeks of the screening visit and within up to 6 months after the date of hospitalization for HF or treatment with IV diuretic for HF, and randomization will be stratified according to region and heart rhythm at baseline ECG.

Region

- Americas
- Europe (incl. Israel and South Africa)
- Asia/Pacific (including Australia)

Heart rhythm

- Atrial fibrillation (defined as atrial fibrillation or atrial flutter in baseline ECG)
- Sinus rhythm (defined as no atrial fibrillation and no atrial flutter in baseline ECG)

To avoid over-representation of patients with atrial fibrillation (AF) in the trial, randomization of patients with AF on their baseline ECG may be stopped at the discretion of the Steering Committee when this randomized cohort comprises approximately 40% of the total planned randomized population. The exact proportion of patients randomized with AF will be determined by the Steering Committee following a review of the blinded baseline clinical characteristics of this group compared to those without AF.

7.4 Dosage and administration

Patients will take two tablets once daily preferably in the morning with food. The starting dose will be 2.5 mg of vericiguat or matching placebo.

Titration steps at 2, 4 and 6 weeks include sham titration in placebo arm. Titration step at 6 weeks includes sham titration in 10 mg arm. The maximal dose of vericiguat is 10 mg o.d. in the 10 mg treatment arm, and 15 mg (5 mg + 10 mg tablet) o.d. in the 15 mg arm ([Table 7-3](#)). For justification of dose selection see [Section 3.2.1](#).

Table 7-3: Dosing plan

Dose step	Arm		
	Placebo	10 mg target dose	15 mg target dose
1	placebo	2.5 mg	2.5 mg
2	placebo	5 mg	5 mg
3	placebo	10 mg	10 mg
4	placebo	10 mg	15 mg

Titration will be based on systolic blood pressure (SBP) measurement, before intake of the study drug as follows:

- **Increase dose:** if SBP \geq 100 mmHg and SBP decrease is \leq 20 mmHg from previous visit, and not yet on highest dose
- **Maintain dose:** if SBP is between 90 mmHg and <100 mmHg, or SBP \geq 100 mmHg and SBP decrease is >20 mmHg from previous visit, or if already on highest dose step (after 3 uptitrations)
- **Decrease the dose:** if SBP <90 mmHg without symptoms of hypotension if on dose steps 2-4 (see [Table 7-3](#)) >2.5 mg, or temporarily interrupt if on 2.5 mg (starting dose or after down titration from a higher dose)
- **Interrupt the dose:** if SBP <90 mmHg with symptoms of hypotension

Dose decrease is possible at any time if the physician feels this is necessary for safety reasons.

The first dose of trial treatment will be administered at the trial site at the randomization visit. Subsequent dosing will be performed once daily preferably in the morning by the patient at approximately the same time each day. Patients will be instructed to take vericiguat with food.

Resumption of study drug after temporary interruption

Upon temporary interruption of the study drug due to intolerance, intake should be resumed as soon as medically justified at the discretion of the investigator. There is no defined maximum time limit for temporary treatment interruption. In all cases, the reason for study drug interruption or permanent study drug discontinuation must be recorded in the eCRF and in the patient's medical records. Titration rules following restart of study drug after temporary interruption of study drug are as follows:

- If restart before visit 5 (week 6): Restart at a scheduled visit and titrate according to the intervals in [Table 7-4](#).
- If restart after visit 5 (week 6) restart as soon as possible (with an unscheduled visit if required) and up-titrate according to [Table 7-4](#). Patient will then resume the planned visit schedule. Unscheduled clinic and/or phone contacts can be conducted at the discretion of the investigator. The titration steps must be at least 11 days apart, and if the period between resumption and the next scheduled visit is more than 17 (14+3) days, the patient can attend an unscheduled visit.

Table 7-4: Resumption of study drug intake

Dose step at time of interruption	(mg) at time of interruption	Length of interruption	Restart dose	1 st titration (14±3 days after resumption)	2 nd titration (28±3 days after resumption)	3 rd titration (42±3 days after resumption)
1	Plc or 2.5	Any	Plc or 2.5	Plc or 5	Plc or 10	Plc or 10 or 15
2	Plc or 5	Any	Plc or 2.5	Plc or 5	Plc or 10	Plc or 10 or 15
3	Plc or 10	>5 days	Plc or 2.5	Plc or 5	Plc or 10	Plc or 10 or 15
		≤5 days	Plc or 5	Plc or 10	Plc or 10 or 15	NA ^a
4	Plc or 10 or 15	>5 days	Plc or 2.5	Plc or 5	Plc or 10	Plc or 10 or 15
		≤5 days	Plc or 5	Plc or 10	Plc or 10 or 15	NA ^a

a highest dose achieved in the second titration

NA, not applicable; Plc, placebo

For follow-up of patients after discontinuation see Section 9.1

7.5 Blinding

Tablets containing 2.5 mg and 5 mg vericiguat and the respective matching placebo tablets will be identical in appearance. 10 mg vericiguat and matching placebo to 10 mg tablets will be identical in appearance. The packaging and labeling are designed to maintain the blinding of the investigator's team and to the patients. The study data will remain blinded for each treatment group, until database lock and authorization of data release.

Unblinding

In compliance with applicable regulations, in the event of a SUSAR (see Section 9.6.1.5) related to the blinded treatment, the patient's treatment code will usually be unblinded before reporting to the health authorities. Notifications of ethic committees and investigators will be done according to all applicable regulations (see Section 9.6.1.4).

In this study, the following events are outcome events and will be considered as disease related in the defined study population. For the purposes of this trial, these events will not be subject to systematic unblinding and expedited reporting process, if reported as serious adverse drug reactions.

- Acute heart failure
- Chronic heart failure
- Worsening chronic heart failure
- Cardiac arrest
- Myocardial Infarction
- Stroke
- CV death

These events will be captured in the eCRF, and will undergo regular central adjudication by central CEC, and unblinded DMC review. If an event submitted for adjudication is determined by the CEC not to meet the endpoint criteria in the CEC charter and meets seriousness criteria, it will then be subject to expedited reporting (as appropriate, based upon both investigator and Bayer company causality assessment of drug relationship, as required by local legislation).

Emergency unblinding by the investigator

In case of emergency or any finding that requires unblinding, the investigator will be able to break the blind for an individual patient via IxRS according to the unblinding procedure implemented. This will allow breaking the blind for an individual patient without impairing the study as a whole unless safety findings required unblinding.

The code can be broken by the investigator, or other responsible person, when knowledge of the patient's treatment is required for the clinical management of the patient. Whenever possible, the sponsor is to be contacted to discuss the case before the code is broken. If it becomes necessary to know the individual treatment during the study and thus to break the code for that patient, the date, time, and reason are to be recorded in the patient's medical notes and relevant eCRF page. The investigator is required to promptly document and explain to the sponsor any premature unblinding (e.g. unblinding due to a serious adverse event) of the study treatment.

Unblinding for ongoing safety monitoring

To allow ongoing safety monitoring during the conduct of the study by an external DMC, members of the Committee will receive unblinded safety data. The involvement of an external Statistical Analysis Center in this process will ensure that unblinded information is not available for third parties. Details of the process are described in the DMC charter.

7.6 Drug logistics and accountability

All study drugs will be stored at the investigational site in accordance with GCP and GMP requirements and the instructions given by the clinical supplies department of the sponsor (or its affiliate/contract research organization), and will be inaccessible to unauthorized personnel. Special storage conditions and a complete record of batch numbers and expiry dates can be found in the sponsor's study file; the site-relevant elements of this information will be available in the investigator site file. On the day of receipt, the responsible site personnel will confirm receipt of study drug via IxRS. The personnel will use the study drug only within the framework of this clinical study and in accordance with this protocol. Receipt, distribution, return and destruction (if any) of the study drug must be properly documented according to the sponsor's agreed and specified procedures.

Written instructions on medication destruction will be made available to affected parties as applicable.

If performing drug accountability implies a potential risk of contamination, a safety process/guidance for handling returned study drug will be provided.

7.7 Treatment compliance

To monitor compliance, completing a drug dispensing log for each patient will be required. Overall compliance with study drug intake should be between 80% and 120% of the scheduled study drug intake at the end of study drug treatment. The date of dispensing the study drug to the patient will be documented.

Study drug will be dispensed at Visit 2, Visit 3, Visit 4, Visit 5, Visit 6, Visit 7 and Visit 8. Patients should return all remaining unused study drug at each visit.

Accountability will be determined by tablet count at each visit. To facilitate this, patients must be instructed to return all of the study drug packaging including unused study drug and empty packaging.

Any discrepancies between actual and expected amount of returned study medication must be discussed with the patient at the time of the visit, and any explanation must be documented in the source records as well as in the eCRF.

8. Non-study therapy

8.1 Prior and concomitant therapy

Permitted background treatment

- Diuretics are recommended in congested patients in order to alleviate symptoms and signs (5).
- Treatment of comorbidities like hypertension, coronary and vascular diseases, hyperlipidemia, diabetes, atrial fibrillation and other arrhythmias should follow the local/regional Guidelines. Any dose adaptations, addition, changed or added route of administration, omission or cessation of concomitant therapy including diuretics, anti-hypertensives such as ACE inhibitors, ARB, or rate control such as β blockers and digoxin are possible whenever deemed necessary by the investigator irrespective of blinded titration of the study drug.

Prohibited prior and concomitant medications:

- Nitrates or NO donors including isosorbide dinitrate, isosorbide 5-mononitrate, pentaerythritol tetranitrate, nicorandil, NTG and molsidomine: all routes are not allowed during study drug treatment; IV therapy with nitrates or NO donors is only allowed until 24 h prior to randomization.

It is recommended that nitrates should not be administered to any patient previously on study drug earlier than 3 days after the last dose of study drug. Should there be an urgent need for nitrate administration, they should be administered in a monitored inpatient setting.
- PDE5 inhibitors: Sildenafil and Vardenafil are allowed only until 24 h prior to randomization, Tadalafil until 48 h prior to randomization.
- sGC stimulators other than the study drug are not allowed during study drug treatment

8.2 Post-study therapy

The investigator must provide follow-up medical care for all patients who complete the study or who are prematurely withdrawn from the study, or must refer them for appropriate ongoing care as required.

Clinical Study Protocol
No. BAY 1021189 / 19334

22 FEB 2018

Version no. 1.0

Page: 36 of 81

9. Procedures and variables

9.1 Tabular schedule of evaluations

Table 9-1: Tabular schedule of assessments

Trial Periods	Screening ^a	Base-line	Titration / Sham titration		Treatment			End of treatment	Safety Follow-Up ^b	Premature Treatment Discontinuation	
			3	4	5	6	7			11	12
Visit Number	1	2						9	10		
Week			2	4	6	8	12	18	24	28	
Visit Window (Days)	-28-1	1	14±3	28±3	42±3	56±3	84±3	126±3	168±3	196±7	At time of permanent treatment discon 28±7 days after last dose
• Informed consent main study	•										
• Demographic data											
• Medical and surgical history											
Optional - Informed consent for pharmacogenetic research	• ^c										
Optional - Informed consent for accelerometry	•										
Concomitant medication	•	•	•	•	•	•	•	•	•	•	•
Inclusion / exclusion criteria	•	•									
Urine pregnancy test (local) ^g	•	•				•					
Randomization (IxRS)		•									
ePRO: KCCQ, PGIC ^d , PGIS, EQ-5D-5L		•	•	•	•	•	•	•	• ^e	•	• ^e
Fried Frailty score		•							•		•
NYHA class	•	•	•	•	•	•	•	•	•	•	•
Blood pressure, pulse rate ^f	•	•	•	•	•	•	•	•	•	•	•
ECG		• ^g						• ^h			• ⁱ
Only in patients eligible for PK/QT assessment ^j	ECG	• ⁱ		• ⁱ				• ⁱ			
	PK sample predose				•			•			
	PK sample 1-2 h, and 3-6h post	• ^k		•				•			
6 MWT	•	•				•		•	•	•	•
Local lab blood sample ^l	•										
Central lab blood sample ^m		•			•			• ^s			•
Optional pharmacogenetic research blood sample		• ^c									
Physical exam, weight, height ⁿ	•	•	•	•	•	•	•	•	•	•	•
Adverse events	•	•	•	•	•	•	•	•	•	•	•
Drug accountability ^o			•	•	•	•	•	•			•
Dispense study drug		•	•	•	•	•	•	•			
Optional uptitration ^p						• ^t	• ^u	• ^t	• ^u		
Optional accelerometry	• ^t	• ^u				• ^t	• ^u	• ^t	• ^u		

Footnotes:

- a. Can start as early as at time of hospitalization or IV diuretic treatment for HF or up to 6 months after. Should start no more than 4 weeks before randomization. Screening visit and baseline visit can take place on the same day.
- b. In case of premature discontinuation of study treatment, vital status will be collected at week 28 by any method (e.g. via telephone call or e-mail), unless the patient has specifically withdrawn consent for further study follow-up.
- c. Optional pharmacogenetic informed consent and blood collection may also be performed at a later visit. Blood sample for genetic analysis will only be taken if the patient signed the separate consent for the pharmacogenetic research study.
- d. Not performed at baseline visit.
- e. Only KCCQ and EQ-5D-5L performed at visit 10 and 12.
- f. 3 measurements, 2 min apart; measurements are taken prior to study drug intake. Additional measurement at 2h ± 15 min post study drug intake will be performed only at visit 2, and at visits 5-8 if dose is uptitrated from dose step 3 to step 4.
- g. Assessment of eligibility for PK/QT assessment.

Clinical Study Protocol
No. BAY 1021189 / 19334

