22 FEB 2018

Version no. 1.0

Page: 37 of 81

- h. Only for patients not eligible for QT assessment
- i. Central 12-lead ECGs should be recorded only in patients eligible for PK/QT assessment, just before the collection of the blood sample for PK, to enable PK/QT assessments. Exact date and time of the ECG recording and date and time of last study drug intake (either at home on the day before the sample or at site) must be documented.
- j. In case the PK sample at the specified visits cannot be obtained at a specified time point, 12-lead ECG and the PK sample can be taken at the subsequent (scheduled or unscheduled) visits. Exact collection date and time of the PK samples and date and time of last study drug intake before PK sampling (either at home on the day before the sample or at site) must be documented.
- k. Only PK sample 1-2h post study drug will be collected at this visit.
- l. Only if not available within 30 days prior to randomization for eligibility, creatinine and NT-proBNP or BNP (or both if available)
- m. NT-proBNP, clinical chemistry, hematology, coagulation, biomarker testing, and other laboratory tests (for full list see Section 9.7.1.2)
- n. Full physical examination to be performed at Visit 1 and 2. Focused cardiovascular examination to be performed in all other visits. Height will be only measured once at the screening visit. Automatic calculation of body mass index (BMI) in the electronic case report form (eCRF) will use this result.
- o. Collect unused study drug.
- p. In case of temporary discontinuation or dose modification after the titration period. An unscheduled visit is possible if the period between resumption and the next scheduled visit is more than 17 days. Time between uptitration steps must be no less than 11 days.
- q. A local lab urine or serum pregnancy test will be conducted for women of childbearing potential according to local procedures. If required by national / institutional regulations, a serum or urine pregnancy test in patients of childbearing potential should be performed more often (e.g. at every visit).
- r. In case of premature discontinuation, ECG is performed as a safety measure.
- s. PK sample predose will be collected together with the central lab sample for all patients.
- t. Only for patients participating in the optional accelerometry substudy, activity tracking devices are planned to be handed out as specified in the accelerometry procedure manual.

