9.2.8 Visit 8 – Day 126±3 (Week 18)

Patients need to come for this visit without taking the morning dose of the study drug (this applies only for the study drug. All others medications shall be taken as scheduled)

- KCCQ, EQ-5D-5L, PGIC/S (see Section [9.4](#))
- Assessment of NYHA class
- Concomitant medications (see Section [8.1](#))
- Adverse events (see Section [9.6.1](#))
- Physical examination
- Vital signs in sitting position (BP and pulse rate). See Section [9.7.5](#)
- Drug accountability, and collect unused study drug.
- Optional uptitration/sham titration if not yet on target dose, dispense study drug in accordance with dosing regimen for the 6 week interval until Visit 9 and instruct the patient on how to take the study drug.

- Patient to take the study drug (exact time of intake must be documented)
- Only in case of uptitration from dose step 3 to dose step 4, 2 h ± 15 min after study drug intake: Vital signs (BP and pulse rate). See Section [9.7.5](#).
- Schedule Visit 9 for Day 168±7
- For PK sampling at visit 9: Remind the patient to report the date and time of the last study drug intake the day before visit 9.
- Only for patients participating in the optional accelerometry substudy: activity tracking devices are planned to be handed out with instructions to use as specified in the accelerometry procedure manual.

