9.7.5 Vital signs

BP and pulse rate measurements will be performed at specific visits. For details see Section [9.2](#).

Accurate measurement of blood pressure is essential to guide dose titration management and to detect potential safety signals during the trial. A number of factors related to the patient can cause significant deviations in measured blood pressure. These include room temperature, exercise, alcohol or nicotine consumption, positioning of the arm, muscle tension, bladder distension, talking, and background noise.

Blood pressure and pulse rate should be measured under the following conditions:

- Measurement of pulse rate and blood pressure must be conducted after 10 minute resting period with patient comfortably seated in a chair with the legs uncrossed and the back and arm supported. Measurements should not be made while the patient is on an examining table. The patient should be instructed to relax as much as possible and to not talk during the measurement procedure
- The examiner should ensure that the middle of the cuff on the upper arm is at the level of the right atrium (the mid-point of the sternum).
- The patient should be asked to remove all clothing that covers the location of cuff placement.
- The same examiner should assess the patient at all subsequent visits and use the same device under same external conditions.
- The protocol requires 3 measurements – approximately 2 min apart (means will be calculated in the eCRF). Please record the time, positioning and arm used for each measurement

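### The 2-hour post-dose BP/pulse check for a step 3 to step 4 increase is tied to Visits 5-8, although the restart rules leave room for that increase at an unscheduled visit

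*Protocol*

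**What the plan says.** **The check.** Protocol Table 9-1 footnote f says the post-dose BP/pulse measurement "will be performed only at visit 2, and at visits 5-8 if dose is uptitrated from dose step 3 to step 4". Sections 9.2.5 to 9.2.8 repeat the condition visit by visit; at Visit 8 it reads "Only in case of uptitration from dose step 3 to dose step 4, 2 h ± 15 min after study drug intake". Section 9.7.5 says "BP and pulse rate measurements will be performed at specific visits" and refers back to section 9.2, which describes no unscheduled visit. The Visit 2 reading covers the starting dose. The increases at Visits 3 and 4 have no post-dose reading.

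**Restart after an interruption.** For a restart after Visit 5, section 7.4 says to "restart as soon as possible (with an unscheduled visit if required) and up-titrate according to" Table 7-4. It adds that "if the period between resumption and the next scheduled visit is more than 17 (14+3) days, the patient can attend an unscheduled visit". Footnote p, attached to the optional up-titration row, says "An unscheduled visit is possible if the period between resumption and the next scheduled visit is more than 17 days". The synopsis has a parallel sentence directly after the one on re-up-titration. It says that the patient should attend, although its day limits are garbled. Section 7.1 adds that "Reasons for dose modifications (maintenance, increase, decrease, or interruption) will be collected at all planned or unscheduled visits".

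**Text pointing the other way.** The next sentence of section 7.1, repeated in the synopsis, names scheduled visits as a place for re-up-titration after an interruption or dose reduction. It does not mention unscheduled visits, either to allow or to exclude them.

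**The concern.** The sponsor attached a post-dose reading to one increase only, step 3 to step 4. In the 15 mg arm this is the move from 10 mg to 15 mg; in the other two arms it is a sham. Section 3.3 says there are no existing data at 15 mg in heart failure and that the hypotension and syncope risks at this dose still need to be characterized. The reading is tied to visit numbers, not to the dose step, and footnote f uses the word *only*. A site that makes the same increase at an unscheduled visit after an interruption could follow the protocol exactly and omit the reading. For a 15 mg arm patient who had not yet reached step 4, that would be the first 15 mg dose.

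**Working it through.** The plan gives no figure to reproduce here. The check is whether the protocol's own timing can place step 4 outside Visits 5-8.

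**Inputs**
- Table 7-4, interruption of at most 5 days from step 3: restart at step 2, step 3 at 14 ± 3 days after resumption, step 4 at 28 ± 3 days.
- Visit 7 is Day 84 ± 3 (Days 81-87) and Visit 8 is Day 126 ± 3 (Days 123-129).
- Visit 9 is Day 168 ± 7 in section 9.2.9 (Days 161-175) and ± 3 in Table 9-1 (Days 165-171).
- Section 7.4: titration steps at least 11 days apart; an unscheduled visit is available if the next scheduled visit is more than 17 days after resumption.

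**If the Table 7-4 intervals are followed**

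Step 4 window = (earliest restart + 25) to (latest restart + 31).

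| Restart | Nominal step 3 | Nominal step 4 | Step 4 with windows | Next scheduled visit opens |
|---|---|---|---|---|
| Visit 7 | 84 + 14 = Day 98 | 84 + 28 = Day 112 | 81 + 25 = 106 to 87 + 31 = 118 | Day 123 (Visit 8) |
| Visit 8 | 126 + 14 = Day 140 | 126 + 28 = Day 154 | 123 + 25 = 148 to 129 + 31 = 160 | Day 161 at the earliest (Visit 9) |

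The shortest time from resumption to the next scheduled visit is 123 − 87 = 36 days or 161 − 129 = 32 days. Both exceed 17, so unscheduled visits are available. In both cases step 4 falls between scheduled visits, where no check is required.

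**If the step 4 increase waits for a scheduled visit**
- Visit 7 restart, with an unscheduled visit used for the first titration only: step 3 at about Day 98 and step 4 at Visit 8, where the check applies. That is 123 − 87 = 36 to 129 − 81 = 48 days after resumption, later than the 25-31 days in Table 7-4.
- Visit 8 restart: no return to step 4, because Visit 9 is end of treatment and section 9.2.9 lists no up-titration.
- If unscheduled visits are not used for titration at all, neither restart reaches step 4 again: the first gets to step 3 at Visit 8, and the second stays at step 2.

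None of these routes gives an unchecked step 4.

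**Other restart days.** Each restart day from Day 43 was tested, keeping step 4 windows that open before Day 161 and using nominal dates for the next visit. For interruptions of at most 5 days, 26 restart days have a step 4 window that misses Visits 6-8 and a next scheduled visit more than 17 days away. For longer interruptions (step 4 at 42 ± 3 days) there are 29. These counts are calendar days, not patients. They show only that the two worked cases are not isolated.

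**The case against.** The strongest reply is that the protocol may not intend step 4 at an unscheduled visit. The sentence in section 7.1 and the synopsis on where re-up-titration happens names scheduled visits. Section 7.4 speaks of one unscheduled visit, says the patient *can* attend it, and returns the patient to the planned schedule. It sets a minimum spacing of 11 days but does not call the Table 7-4 windows binding upper limits. This stands as far as it goes: the gap depends on how these passages are read. It does not close the gap, because no passage excludes an unscheduled step 4 or limits unscheduled visits to the first titration. A site that keeps to the Table 7-4 intervals in the worked cases cannot do so at scheduled visits. Section 7.1 also gives reaching and maintaining the target dose as the protocol's intention.

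A second reply is that the reading has no consequence. It has no action threshold, and the SAP names no analysis of it. Pre-dose SBP rules govern every titration, symptomatic hypotension and syncope are reported within 24 hours, and investigators may take extra readings. All this is correct and keeps the point small. Section 7.4 nevertheless lets the physician lower the dose at any time for safety, so a low reading could be acted on.

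A reader might also take footnote j as evidence of an oversight, since it says that "12-lead ECG and the PK sample can be taken at the subsequent (scheduled or unscheduled) visits". That would be too strong. Footnote j deals with making up missed samples; it is not a rule on safety checks at dose increases.

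**Conclusion.** The point holds as a minor, conditional safety-monitoring gap. The check is limited to Visits 5-8, the restart rules leave room for the same increase elsewhere, and no passage requires the check there.

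It rests on two assumptions: that the Table 7-4 intervals are followed, and that unscheduled visits may serve the second titration as well as the first. The text permits the second assumption but does not state it. A reader might infer that the protocol directs an unchecked step 4, or that step 4 in the worked cases can never coincide with a scheduled visit. The documents support neither. Section 7.4 is permissive, and a Visit 7 restart can reach step 4 at Visit 8 with the check.

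A first 15 mg dose without the check can arise only in the 15 mg arm (245 of 735 planned patients), and there only in patients who had not reached step 4 before the interruption. The documents give no interruption rate, so the number is unknown; it is probably small. Sample size, alpha and every efficacy result are unaffected.

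**What to change.** Tie the check to the dose step instead of the visit number. Reword footnote f so that the 2 h ± 15 min BP/pulse measurement is done at Visit 2 and at any visit, scheduled or unscheduled, where the dose goes from step 3 to step 4. Add one sentence to section 7.4 saying the same for re-titration after an interruption. Apply it in all three arms, including sham steps, so that the blind is kept.

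The cost is one footnote, one sentence, and about 2 more hours on site for each patient who takes this step at an unscheduled visit.
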